4.3. Treatment Arms and Duration

- A screening period of up to 4 weeks, will be followed by a 12 week treatment period (dosing with GSK3196165 or placebo) then a follow up period, completing on week 22. The total study duration for an individual subject will be approximately 26 weeks.

- The Study consists of 2 arms: treatment with GSK3196165 or placebo will be given as a single subcutaneous injection (shielded to subjects) to the abdomen or thigh, by an unblinded administrator weekly for 5 injections, from Week 0 to Week 4 (Days 1, 8, 15, 22, 29), then every other week for 3 further injections, from Week 6 until Week 10 (Days 43, 57 and 71).
- In total, each subject will receive up to 8 doses of study treatment.

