5. SELECTION OF STUDY POPULATION AND WITHDRAWAL CRITERIA

Specific information regarding warnings, precautions, contraindications, adverse events, and other pertinent information on the GSK investigational product or other study treatment that may impact subject eligibility is provided in the IB [GSK Document Number [2014N190256_00](#)] and IB supplement [GSK Document Number [2015N226819_00](#)].

Deviations from inclusion and exclusion criteria are not allowed because they can potentially jeopardize the scientific integrity of the study, regulatory acceptability or subject safety. Therefore, adherence to the criteria as specified in the protocol is essential. In addition, investigators are expected to assess vaccination status, including against influenza and pneumococcus according to local guidelines.

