10. ALT >2xULN and bilirubin >1.5xULN (isolated bilirubin >1.5xULN is acceptable if bilirubin is fractionated and direct bilirubin <35%).
11. Current or chronic history of liver disease, or known hepatic or biliary abnormalities (with the exception of Gilbert's syndrome or asymptomatic gallstones)
12. A history of malignant neoplasm within the last 10 years or breast cancer within the last 20 years, except for non-melanoma skin cancers that have been excised and cured or carcinoma *in situ* of the uterine cervix.
13. Kidney disease: Current or history of renal disease, or estimated creatinine clearance <60 mL/min/1.73m² or serum creatinine >1.5xULN within 28 days of Day 1.
14. Hereditary or acquired immunodeficiency disorder, including immunoglobulin deficiency.
15. History of infected joint prosthesis at any time, with the prosthesis still *in situ*. History of leg ulcers, catheters, chronic sinusitis or recurrent chest or urinary tract infections.
16. Active infections, or history of recurrent infections (excluding recurrent fungal infections of the nail bed), or have required management of acute or chronic infections, as follows:
 - a. Currently on any suppressive therapy for a chronic infection (such as tuberculosis, pneumocystis, cytomegalovirus, herpes simplex virus, herpes zoster and atypical mycobacteria).

OR

- b. Hospitalization for treatment of infection within 26 weeks of Day 1.

OR

- c. Use of parenteral (IV or IM) antimicrobials (antibacterials, antivirals, antifungals, or antiparasitic agents) within 26 weeks of Day 1 or oral antimicrobials within 14 days of Day 1.

17. A vaccination (live or attenuated) within 30 days of Day 1 or BCG vaccination within 365 days of Day 1, or a live vaccination planned during the course of the study.
18. Any surgical procedure, including bone or joint surgery/synovectomy within 12 weeks prior to Day 1 or any planned surgery within the duration of the study or follow-up period.
19. Contraindication to MRI scanning (as assessed by local MRI safety questionnaire) which includes but not limited to:
 - a. Intracranial aneurysm clips (except Sugita) or other metallic objects,
 - b. History of intra-orbital metal fragments that have not been removed by a medical professional,
 - c. Pacemakers or other implanted cardiac rhythm management devices and non-MR compatible heart valves,
 - d. Inner ear implants, except MR-conditional implants scanned within manufacturer guidelines,

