5.3.2. Re-Testing – Laboratory Exclusion

If a subject fails any of the laboratory exclusion criteria, the test may be repeated twice within the screening period. If the subject fails the laboratory criteria for a third time they will be considered a screen failure; these subjects may be re-screened as described in Section [5.3.1](#).

If a blood sample has to be withdrawn due to sample handling problems, breakage or sample integrity, this is not considered a re-testing.

Further details regarding the procedure for re-testing may be found in the SRM.

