6.10.1. Permitted Medications and Non-Drug Therapies

The only permitted concomitant medication for the duration of this study is Paracetamol (acetaminophen) which may be taken on an as needed basis up to 4g/day or to the maximum permitted under local label.

Any use of Paracetamol (acetaminophen) will be recorded as concomitant medication. Subjects will record use of Paracetamol (acetaminophen) for hand pain on a daily basis.

Use of any other concomitant medications by subjects will be assessed during study visits.

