12.2. Appendix 2 – Liver Safety Required Actions and Follow up Assessments

Phase II liver chemistry stopping and increased monitoring criteria have been designed to assure subject safety and evaluate liver event etiology (in alignment with the FDA premarketing clinical liver safety guidance).

<http://www.fda.gov/downloads/Drugs/GuidanceComplianceRegulatoryInformation/Guidances/UCM174090.pdf>.

Phase II liver chemistry stopping criteria and required follow up assessments

| Liver Chemistry Stopping Criteria – Liver Stopping Event | |
|--|---|
| ALT-absolute | ALT \geq 5xULN |
| ALT Increase | ALT \geq 3xULN persists for \geq 4 weeks |
| Bilirubin^{1, 2} | ALT \geq 3xULN and bilirubin \geq 2xULN (>35% direct bilirubin) |
| INR² | ALT \geq 3xULN and INR>1.5, if INR measured |
| Cannot Monitor | ALT \geq 3xULN and cannot be monitored weekly for 4 weeks |
| Symptomatic³ | ALT \geq 3xULN associated with symptoms (new or worsening) believed to be related to liver injury or hypersensitivity |

| Required Actions and Follow up Assessments following ANY Liver Stopping Event | |
|--|--|
| Actions | Follow Up Assessments |
| 
 Immediately discontinue study treatment Report the event to GSK within 24 hours Complete the liver event CRF and complete an SAE data collection tool if the event also meets the criteria for an SAE² Perform liver event follow up assessments Monitor the subject until liver chemistries resolve, stabilize, or return to within baseline (see MONITORING below) Do not restart/rechallenge subject with study treatment unless allowed per protocol and GSK Medical Governance approval is granted (refer to Section 5.4.1.1.) If restart/rechallenge not allowed per protocol or not granted, permanently discontinue study | 
 Viral hepatitis serology⁴ Blood sample for pharmacokinetic (PK) analysis, obtained within a week after last dose⁵ Serum creatine phosphokinase (CPK) and lactate dehydrogenase (LDH). Fractionate bilirubin, if total bilirubin\geq2xULN Obtain complete blood count with differential to assess eosinophilia Record the appearance or worsening of clinical symptoms of liver injury, or hypersensitivity, on the AE report form Record use of concomitant medications on the concomitant medications report |

| | |
|--|---|

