| 
treatment and may continue subject in the study for any protocol specified follow up assessments
 
MONITORING:
 
For bilirubin or INR criteria:
 
 Repeat liver chemistries (include ALT, AST, alkaline phosphatase, bilirubin) and perform liver event follow up assessments within 24 hrs Monitor subjects twice weekly until liver chemistries resolve, stabilize or return to within baseline A specialist or hepatology consultation is recommended 
For All other criteria:
 
 Repeat liver chemistries (include ALT, AST, alkaline phosphatase, bilirubin) and perform liver event follow up assessments within 24-72 hrs Monitor subjects weekly until liver chemistries resolve, stabilize or return to within baseline | 
form including acetaminophen, herbal remedies, other over the counter medications.
 
 Record alcohol use on the liver event alcohol intake case report form 
For bilirubin or INR criteria:
 
 Anti-nuclear antibody, anti-smooth muscle antibody, Type 1 anti-liver kidney microsomal antibodies, and quantitative total immunoglobulin G (IgG or gamma globulins). Serum acetaminophen adduct HPLC assay (quantifies potential acetaminophen contribution to liver injury in subjects with definite or likely acetaminophen use in the preceding week [James, 2009]). NOTE: not required in China Liver imaging (ultrasound, magnetic resonance, or computerised tomography) and /or liver biopsy to evaluate liver disease: complete Liver Imaging and/or Liver Biopsy CRF forms. |

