| ALT \geq 3xULN and <5xULN and bilirubin <2xULN, without symptoms believed to be related to liver injury or hypersensitivity, and who can be monitored weekly for 4 weeks | 
 Notify the GSK medical monitor within 24 hours of learning of the abnormality to discuss subject safety. Subject can continue study treatment Subject must return weekly for repeat liver chemistries (ALT, AST, alkaline phosphatase, bilirubin) until they resolve, stabilise or return to within baseline If at any time subject meets the liver chemistry stopping criteria, proceed as described above If, after 4 weeks of monitoring, ALT <3xULN and bilirubin <2xULN, monitor subjects twice monthly until liver chemistries normalize or return to within baseline. |

References

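### Exclusion 10 joins its ALT and bilirubin limits with *and*, which contradicts its own bracket and, read literally, admits an isolated ALT above 2xULN

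*Protocol*

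**What the plan says.** Section 5.2 excludes a subject who meets any one of its numbered criteria. Number 10 is the only one with an ALT threshold: "ALT >2xULN and bilirubin >1.5xULN (isolated bilirubin >1.5xULN is acceptable if bilirubin is fractionated and direct bilirubin <35" per cent, where the bracket closes. Neither Amendment 01 nor Amendment 02 lists a change to it, and no other section restates it with a different connective.

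Section 5 allows no deviations from the entry criteria and says that "adherence to the criteria as specified in the protocol is essential".

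Appendix 2 (section 12.2) sets the on-study liver rules. ALT from 3xULN to below 5xULN, with bilirubin below 2xULN, no relevant symptoms and weekly monitoring feasible, is a monitoring event: "Subject can continue study treatment Subject must return weekly for repeat liver chemistries". ALT of 5xULN or more is a stopping event. So is ALT that at "3xULN persists for" four weeks or longer.

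Section 5.3.2 says of a failed laboratory criterion that "the test may be repeated twice within the screening period".

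**The concern.** The criterion contradicts itself. If both abnormalities are needed for exclusion, a subject with raised bilirubin alone is never excluded, and there is nothing for the bracket to permit. If the bracket means what it says, either abnormality alone must exclude, and *and* is the wrong word.

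This is a working safety entry rule, applied to every screened subject. Two sites could handle the same unexplained ALT of, say, 2.5xULN in opposite ways, and each could defend its decision from the text. Taken literally, the rule also lets a subject begin an investigational antibody with a transaminase value that the same protocol treats, once on study, as a reason for weekly chemistry and notification of the medical monitor.

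**Working it through.** The plan states no figure on this point, so the check is a comparison of readings.

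**Inputs.** From exclusion 10: ALT limit 2xULN, bilirubin limit 1.5xULN, and the bracket's condition (fractionated, direct bilirubin below 35%). ALT has two states. Bilirubin has three: not raised; raised with the condition met; raised with the condition not met (unfractionated, or direct 35% or more). This gives 2 x 3 = 6 profiles.

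**Rules.**
- Literal: exclude if ALT is raised *and* bilirubin is raised.
- Bracket-consistent: exclude if ALT is raised *or* bilirubin is raised, except where bilirubin alone is raised and the condition is met.

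| ALT >2xULN | Bilirubin >1.5xULN | Literal *and* | *Or* with bracket |
|---|---|---|---|
| no | no | eligible | eligible |
| no | yes, condition met | eligible | eligible |
| no | yes, condition not met | eligible | **excluded** |
| yes | no | eligible | **excluded** |
| yes | yes, condition met | excluded | excluded |
| yes | yes, condition not met | excluded | excluded |

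**Result.** The literal rule excludes 2 of 6 profiles and the bracket-consistent rule excludes 4 of 6, so they differ on 4 - 2 = 2. Deleting the bracket changes no row of the literal column. Under *or* the bracket changes one row: isolated bilirubin with the condition met becomes eligible. The bracket has a function only under *or*.

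**Do other exclusions close the gap?**
- Number 2 covers significant unstable or uncontrolled disease, including hepatic disease, and turns on the investigator's opinion.
- Number 11 covers liver disease and liver or biliary findings already known, with no ALT figure.
- Number 25 covers Grade 3 or 4 chemistry under CTCAE. The protocol does not give the ALT multiple for Grade 3.
- Numbers 21, 27, 28 and 30 cover alcohol and drug misuse, hepatitis B and C, and the drug and alcohol screen.

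None sets an ALT limit. An unexplained isolated ALT above 2xULN that is below Grade 3, and is not judged to fall under number 2 or 11, passes the list as written.

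**Against the on-study rules.** The monitoring level starts at 3xULN, which is 3/2 = 1.5 times the 2xULN entry limit. Under the literal rule, nothing in number 10 keeps a subject with normal bilirubin below that level.

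**The case against.** The best defence is that the sentence resolves itself. A reading that leaves the bracket empty is the less natural one, and since any listed item excludes, *and* can be taken as naming two separate exclusions. The list is loosely drafted elsewhere: exclusion 24, which asks for negative rheumatoid factor and anti-CCP, would exclude the intended population if read literally. Sites must already read parts of the list by their sense. Number 11 also reaches findings short of active disease, so a screening ALT known before Day 1 arguably falls under it. The risk table in section 4.7.1 names no hepatic risk for the drug, and Appendix 2 provides active monitoring.

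Much of this stands. The intent was very probably *or*, and many sites may apply it. It does not make the wording right. Within other criteria the authors write *or* when they mean alternatives (numbers 9, 13 and 16) and *and/or* in number 27, so *and* in number 10 is naturally read as a conjunction. Number 11 sets no numeric limit and needs interpretation.

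Several stronger inferences are tempting and are not supported:
- A reader might infer that section 5 obliges sites to apply the literal *and*. It forbids deviations, but it does not forbid reading a criterion consistently with its own bracket.
- A reader might infer that only the isolated ALT profile is in dispute. That holds *and* literally for ALT while giving the bracket force for bilirubin, which mixes two readings.
- A reader might try to state how many doses such a subject would receive before the four-week stopping rule applied. Appendix 2 does not say when the four weeks begin. Dosing is "weekly for 5 injections, from Week 0 to Week 4 (Days 1, 8, 15, 22, 29"), so Day 29 is itself a dosing day, and chemistry goes to a central laboratory (section 7.4.9). No firm bound follows.
- A reader might infer that permitted paracetamol ("Paracetamol (acetaminophen) which may be taken on an as needed basis up to 4g/day") makes the gap materially worse. Appendix 2 does include an assay that "quantifies potential acetaminophen contribution to liver injury", so attribution is a recognised question, but the protocol gives nothing from which to size the effect.

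**Conclusion.** The point holds as a wording defect in a safety entry rule. The main clause and the bracket of exclusion 10 are incompatible, and the literal reading admits two of six profiles that the bracket-consistent reading excludes: isolated ALT above 2xULN, and isolated bilirubin above 1.5xULN with the bracket's condition unmet. Sites could diverge, and a subject could enter with ALT at 3xULN or more unless another exclusion applies.

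This rests on two limits. First, how much of the range from 3xULN upward number 25 would catch cannot be settled from the protocol, because the Grade 3 multiple is not given. Second, the protocol gives no frequency for either profile, so the number of subjects affected is unknown and may be small.

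Appendix 2 continues to protect any such subject through weekly chemistry and the stopping rules. Nothing here bears on the sample size, power, significance level or primary analysis.

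**What to change.** In exclusion 10, replace *and* with *or* between the ALT limit and the bilirubin limit. Keep both thresholds and the whole bracket as they stand. Isolated bilirubin with a fractionated direct share below 35% stays eligible, and the two disputed profiles become clearly excluded.

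The cost is one word in the next amendment and possibly a few more screen failures. The two repeat tests already allowed in section 5.3.2 mean that a transient ALT rise need not lose a subject.

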5.2. Exclusion Criteria

A subject will not be eligible for inclusion in this study if *any* of the following criteria apply:

CONCURRENT CONDITIONS/MEDICAL HISTORY (INCLUDES LIVER FUNCTION AND QTc INTERVAL)

1. Pregnant or lactating females.
2. Significant unstable or uncontrolled acute or chronic disease (*e.g.*, cardiovascular including uncompensated congestive cardiac failure NYHA III or IV, myocardial infarction within 12 months, unstable angina pectoris, uncontrolled hypertension, hypercholesterolemia) pulmonary, hematologic, gastrointestinal (including Crohn's Disease or ulcerative colitis), hepatic, renal, neurological, psychiatric, malignancy, endocrinological, immunologic or infectious diseases, which, in the opinion of the investigator, could confound the results of the study or put the subject at undue risk.
3. History of any clinically significant inflammatory disease other than inflammatory HOA, especially, but not limited to, rheumatoid arthritis or spondylarthropathies.
4. Diagnosis of rheumatoid arthritis, fibromyalgia, gout, calcium pyrophosphate deposition disease CPPD, pseudogout, hemochromatosis or other inflammatory rheumatological or autoimmune disorders.
5. Clinical suspicion of, or previous investigation for CPPD or pseudogout, or history of chondrocalcinosis.
6. Any injury, medical or surgical procedure to the affected joint(s) that may interfere with evaluation of the target HOA joint(s).
7. History of any clinically-significant respiratory disease that required treatment and/or follow up under the direction of a physician or any respiratory disease which in the opinion of the Investigator would compromise the ability of the subject to complete the study (*e.g.* interstitial lung disease, such as pulmonary fibrosis, chronic obstructive pulmonary disease [COPD], moderate-severe asthma, bronchiectasis, pneumonitis, pulmonary alveolar proteinosis (PAP), significant exposure to pneumotoxins (*e.g.* inhaled silica).
8. Clinically-significant or unstable (in the opinion of the Investigator) persistent cough or dyspnea that is unexplained.
9. QTc > 450 msec or QTc > 480 msec in subjects with Bundle Branch Block based on averaged values of triplicate electrocardiograms obtained over a brief (*e.g.* 5-10 minute) recording period
 - The QTc is the QT interval corrected for heart rate according to Bazett's formula (QTcB), Fridericia's formula (QTcF), and/or another method, machine-read or

manually over-read.

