 - e. History of claustrophobia which may impact participation

| |
|--|
| CONCOMITANT MEDICATIONS AND NON-DRUG THERAPIES |
|--|

20. Use any of prohibited medications, as listed in Section 6.10.2, throughout the study until after completion of the week 22 follow-up visit. Prohibited medications must be discontinued for the stated time in Section 6.10.2 prior to Day 1.

Note: For patients who need to discontinue prohibited medication > 28 days prior to Day 1, written informed consent for the study must be obtained prior to this discontinuation, however screening assessments other than consent must still occur within the 28 days prior to Day 1.

| |
|-----------------|
| RELEVANT HABITS |
|-----------------|

21. Have current drug or alcohol abuse or dependence, or a history of drug or alcohol abuse or dependence within a year prior to Day 1.

| |
|-------------------|
| CONTRAINdications |
|-------------------|

22. History of sensitivity to any of the study treatments, or components thereof or a history of drug or other allergy that, in the opinion of the investigator or GSK Medical Monitor, contraindicates their participation.
23. Contraindication to gadolinium contrast agent as assessed by the site.

| |
|---|
| DIAGNOSTIC ASSESSMENTS AND OTHER CRITERIA |
|---|

24. Must have negative titer rheumatoid factor (RF) and anti-CCP antibody.
25. Any Grade 3 or 4 hematology or clinical chemistry laboratory abnormality [CTCAE, 2009 v4.0] within 28 days of Day 1.
26. Hemoglobin ≤ 9 g/dL; white blood cell count $\leq 3.0 \times 10^9$ /L; platelet count $\leq 100 \times 10^9$ /L; absolute neutrophil count $\leq 1.5 \times 10^9$ /L; lymphocyte count $\leq 0.8 \times 10^9$ /L within 28 days of Day 1.
27. Presence of hepatitis B surface antigen (HBsAg) and/or presence of hepatitis B core antibody (HBcAb) at screening.
28. Positive hepatitis C antibody test result at screening. Subjects with positive Hepatitis C antibody due to prior resolved disease can be enrolled only if a confirmatory negative Hepatitis C RNA PCR test is obtained.
29. Positive serology for human immunodeficiency virus (HIV) 1 or 2 (within 28 days of Day 1).
30. A positive pre-study drug/alcohol screen.

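### Exclusion criterion 24 is worded as an inclusion requirement, so read literally with its list it bars seronegative subjects: a minor correction

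*Protocol*

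**What the plan says.** All 32 exclusion criteria in Section 5.2 of the protocol stand under one lead-in: "A subject will not be eligible for inclusion in this study if *any* of the following criteria apply". Item 24 in that list reads "Must have negative titer rheumatoid factor (RF) and anti-CCP antibody".

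The other serology items in the list name the abnormal finding. Item 27 names the presence of hepatitis B surface antigen or core antibody, item 28 begins "Positive hepatitis C antibody test result at screening", and item 29 begins "Positive serology for human immunodeficiency virus (HIV) 1 or 2 (within 28 days of Day 1".

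Two further items show which population is meant to be kept out. Item 3 is "History of any clinically significant inflammatory disease other than inflammatory HOA, especially, but not limited to, rheumatoid arthritis or spondylarthropathies". Item 4 is "Diagnosis of rheumatoid arthritis, fibromyalgia, gout, calcium pyrophosphate deposition disease CPPD, pseudogout, hemochromatosis or other inflammatory rheumatological or autoimmune disorders".

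The screening table in Section 7.1.1 schedules RF and ACPA (anti-CCP) on Screening Day 1. Section 5 adds: "Deviations from inclusion and exclusion criteria are not allowed".

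**The concern.** In an exclusion list, each item should describe a state that disqualifies. Item 24 describes the state that qualifies. Combined with the lead-in, its literal meaning is the reverse of what the sponsor evidently wants.

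The item has a real job. Section 5.1 selects subjects for swollen and tender PIP or DIP joints and for signs of inflammation on MRI. The drug is also in development for rheumatoid arthritis (Section 2). A serology rule is presumably there to catch rheumatoid disease that has not yet been diagnosed, although the protocol does not state this purpose.

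Three procedures depend on the wording:

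- Section 5 leaves no formal room to apply the intended rule in place of the written one.
- Section 5.3 requires eligibility criteria to be captured for screen failures.
- Section 5.3.2 allows a test to be repeated twice after a laboratory exclusion criterion is failed. With item 24 as it stands, it is unclear which result counts as failing.

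**Working it through.** The protocol gives no figure to reproduce here, so the main check is logical.

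**Step 1. Apply the lead-in to item 24.** The rule is: if the statement in the item is true of the subject, the subject is ineligible. The statement in item 24 is that RF is negative and anti-CCP is negative.

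| RF | Anti-CCP | Statement true? | Literal result of item 24 | Evident intent |
|---|---|---|---|---|
| negative | negative | yes | excluded | not excluded |
| positive | negative | no | not excluded | excluded |
| negative | positive | no | not excluded | excluded |
| positive | positive | no | not excluded | excluded |

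The literal result is reversed in all four combinations.

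**Step 2. Look for another rule that settles it.**

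- Section 5.1: inclusion criteria 1 to 10 do not mention RF or anti-CCP.
- Section 5.2, items 3 and 4: these act on a history or a diagnosis. A positive result in a subject with neither is not covered.
- Section 7.1.1: the table schedules the tests but gives no required result.
- Appendix 14: Amendment 02 revised inclusion criteria 2, 3 and 5 and exclusion criteria 9 and 19(d). No change to item 24 is listed.

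Item 24 is therefore the only place where the RF and anti-CCP results bear on eligibility.

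**Step 3. Derive the correct exclusion wording.** The negation of *RF negative and anti-CCP negative* is *RF positive or anti-CCP positive*. The connective must change from *and* to *or*. If *and* were kept, subjects positive on only one test (rows 2 and 3) would still not be excluded.

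**Step 4. Bound the effect of one seropositive entry.** With 20 subjects per arm (Section 4.4), one subject is 1/20 = 5% of an arm. The documents give no figure for how differently such a subject would respond. As an assumption, let one on active drug improve by 2 to 5 NRS points more than otherwise:

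- lower end: 2/20 = 0.10 points on the arm mean
- upper end: 5/20 = 0.25 points on the arm mean

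Section 9.2.1 gives a minimal significant difference of about 2 points with 20 per arm and an SD of 3. The shift is 0.10/2 = 5% to 0.25/2 = 12.5% of that.

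**The case against.** The strongest reply is that nobody would misread the item. *Must have* is an instruction, and a seropositive subject plainly fails it. The reversal appears only if the instruction is turned into a description of the subject. On that reading, a trial that takes care to keep rheumatoid arthritis out would turn away every seronegative subject, which no investigator would take as intended. Item 20 in the same list also contains requirement language, so mixed phrasing may be only a lapse of style.

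Other safeguards exist. Inclusion criterion 2 requires the ACR classification of OA. Item 4 reaches other inflammatory rheumatological and autoimmune disorders, not only rheumatoid arthritis. Sections 7.1.1 and 7.2 require the laboratory screening to be passed before the MRI, so the investigator should have the result before randomization.

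Most of this stands, and it limits the practical importance of the point. It does not make the text right. Item 20 opens with a genuine reason for exclusion and only then adds a requirement, whereas item 24 contains the requirement alone. The instruction to pass laboratory screening does not say which RF or anti-CCP result is a pass. That Amendment 02 left item 24 alone is at best weak evidence that no site was confused.

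**Conclusion.** The point holds as a minor drafting error in an operative eligibility rule. Item 24 is inverted when read literally with its lead-in, it conflicts with the direction of items 27 to 29 and the evident purpose of items 3 and 4, and no other text supplies the rule. The realistic consequence is ambiguity in eligibility and screen-failure records and, at most, a rare seropositive entry. Sample size, power and the primary analysis do not change. This rests on the assumption that sites infer the intended meaning, which the wording makes easy.

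A reader might infer three stronger conclusions that the documents do not support:

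- **That all subjects would be misclassified on serology.** This follows only from the literal reading, which sites are unlikely to apply.
- **That eligibility answers in the eCRF are reversed.** The form is not among the documents, so its wording is unknown.
- **That seropositive entries could create an apparent treatment effect.** Allocation is randomized 1:1 and blinded to subject and investigator, so a stray entry is as likely to fall on placebo as on active drug. The bound in the working, 0.10 to 0.25 points for one subject, is small against about 2 points. The rheumatoid arthritis results in Section 2.2.4 concern diagnosed, active disease and chiefly DAS28, not hand pain in seropositive subjects without that diagnosis.

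**What to change.** Make one of two equivalent changes:

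1. Move the present wording of item 24 unchanged to Section 5.1 as an inclusion criterion, where a *must have* item reads correctly.
2. Keep it in Section 5.2 and reword it as *Positive RF or positive anti-CCP antibody at screening*. This keeps the numbering and matches items 28 and 29.

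Whichever is chosen, check that the eligibility question the sites complete carries the same wording. The cost is one line in a protocol amendment and, if needed, the matching form item. No test or visit is added, because RF and anti-CCP are already measured on Screening Day 1, and the intended population does not change.
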